Together these two applications (screen, intervene and train) of the MEAH model have been combined into a single e-learning approach to support the mental health of SHCP and to train SHCP to manage patients in very short time period (under 2 hours). Having completed the SIT approaches we would be able to consider effectiveness of the training during SHCP-patient interactions by focusing further on emotions, adaptation and hope.

It is important to note that all stages of the SIT approach have been developed using electronic resources, and as such the planned study methods are compliant with current legislation on social distancing, whilst being scalable to achieve a wider reach of SHCP across the NHS and other practice settings in the post COVID era across the UK. The additional benefit of this work

¹ Ethical approval was gained from University of Birmingham ethics committee reference: ERN_20-0565.

² Ethical approval was gained from University of Birmingham ethics committee reference: ERN_18-1970B and ERN_18-1970C. Online protocol number: ISRCTN 13368968

is that once trained, SHCP can apply the training at a patient level, or as part of personalised medicine and we would be able to pilot the effectiveness of the training on patients using a multi-centre quasi-experimental design.

Our research to date underpins our rigorously developed e-learning training which has been tested as a proof of concept in a single application and has the potential, following further research to be applied to the NHS and then more globally. The proposed research seeks to combine the above two applications for a novel study that can be offered across all frontline SHCP.

Aims and Objectives

The aim of this study is to investigate the impact of a 2-hour MEAH e-learning training session on depression and anxiety of SHCPs.

Objectives

1. To explore changes in depression and anxiety as a primary outcome measure across three time points (pre-intervention, post intervention, at 12-weeks) for all front-line SHCP during the screening and intervening phase. To compare the intervention and control at the pre-, post- and follow up time points
 2. To identify longer term outcomes for the SHCP intervention group at 6 months
 3. To examine changes in secondary outcome measures on SHCP including quality of life, stigma, communication, hope, and empathy.

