Sampling and sample size; Any SHCP currently studying and working in COVID-19 units. Pilot research identified significant impact on student communication and a medium effect size is expected. Using Cohen's (1988) tables with an alpha of 0.01, $d = 0.5$ (a medium effect) and beta of 0.9 we will recruit 94 SHCP per group to take part in this research. This will give a total of 120 SHCP and we will add in a 10% margin ($n=20$) for dropout or incomplete data. This gives a total of 140 SHCP to be randomised per arm or 280 in total. We will try and ensure a mixed sample with SHCP from different allied health professional groups using purposive sampling.

Sequence generation; Random number calculator with randomly selected block sizes (Efird, 2011).

Allocation concealment; undertaken by e-links not known to the researcher

Sequence generation; We will replicate the pilot research and include a random number calculator with randomly selected block sizes (Efird, 2011). Randomisation undertaken by a member of the research team separate from the study will allocate SHCP to an intervention control group using a random number generator.

Blinded assessor; Only blinded assessment will take place. Before randomisation a blinded assessor (lecturer in physiotherapy or research student) will distribute questionnaires. The pre-recorded e-learning programme has been prepared by [name] who developed and prepared all pilot studies. Following the completion of the training an assessor who is blinded to treatment arm will organise and collect follow-up assessments.

Data collection methods: Before data collection starts SHCP will be shown the information sheet via email and asked to consent (Appendix B). A baseline measurement will take place (Appendix C). The baseline measurement will take place over a secure electronic data capture system called Research Electronic Data Capture (REDCap). Following this, students in each group will receive the training. Once the training is complete students will again fill in the measurement tools using REDCap. The research associate will send out two email reminders to any participant who doesn't fill in the forms.

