Intervention: The SIT intervention will include a single screening interview taking 20 minutes with [name]. Following this the participant will be sent a pre-recorded e-based training session. The lecture takes 45 minutes. The indicative content considers examples of interactions, the science behind the MEAH, the use of screening and how to engage in a brief narrative-based intervention within practice. It has the same components as the pilot studies, although adapted into one training session. The final part of the training for SHCP will include an e-learning presentation. The presentation will provide an analysis of the screening calls. This will reveal the most common difficulties and stories expressed within screening and will

summarise the difficulties that were challenging to adapt to, illustration of how the MEAH is important for this understanding and the most common coping strategies identified (this was undertaken and achieved as part of the pilot research to consolidate learning). The principles are that sharing this information will provide direct access to others experiences which has been associated with enhanced mental health outcomes (Ooms et al., 2016; Soundy et al., 2019). The benefit of this is SHCP can access effective coping strategies that promote mental health and psychological well-being outcomes. This entire process will take a maximum of two hours to complete at a pace and time that is convenient to the participant.

Inactive control group 1: an inactive waiting list control group will be used. Individuals in this group will receive or be offered the SIT intervention at week 12.

Active control group 2: an alternative e-intervention will be used which includes a 45 minutes pre recorded lecture. Individuals in this group will receive or be offered the SIT intervention at week 12.

Outcome measures for SHCP;

See Appendix C for all outcome measures

Demographics; Age, gender, professional group, type of course, year of course. Time experience of working in a COVID-19 setting in months.

Primary outcome measure for SHCP:

The Hospital Anxiety and Depression Scale (HADS: Zigmond and Snaith, 1983). A 14-Item questionnaire that assesses depression and anxiety.

Secondary outcomes measures for SHCP;

(a) The SF-12 Quality of life questionnaire (Ware et al., 1995). A 12-item questionnaire that assesses quality of life.

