24-week intervention group follow up completed by: May 2021 (analysis completed by trials unit other staff costs covered by University)

Follow up publication: June 2021

Other publications: September 2021.

Data management: The research associated will use the University REDCap system to access the data and only work on a University password protected computer.

Statistical methods; For the main study and sub-study descriptive statistics will be used. Confidence intervals will be used to consider change. A factorial ANOVA (a parametric statistical technique which can assess change in one test rather than needing to perform many) will be used to test group differences across outcome measures. An ANOVA will consider the change in scores across time for the intervention group. All qualitative data will be analysed using a thematic analysis (Braun and Clarke, 2006).

Data monitoring: [name] will report any adverse events to University program leader for consideration. Any program leader will be able to stop the study if required. No adverse events were reported across all pilot research. All adverse events will be reported to the steering group committee.

Ethics: We will adhere to the; Research Governance Framework (Department of Health 2005), Declaration of Helsinki (World Health Association, 2013) and University of Birmingham Code of Practice for research (University of Birmingham 2018) and General Data Protection Regulation (2018).

Protocol amendments: [name] will report any protocol amendments.

Consent: the research associate will ensure consent is obtained from participants.

Confidentiality: All data will be stored anonymously on the University of Birmingham computer. Declaration of interest: None are declared.

Access to data: only the research team will have access to the full data.

Ancillary and post-trial care: This will be reported by [name] to program leads if required.

Deliverables

Benefits within the Hospital setting

- Reduced depression and anxiety across SHCP
- Positive changes in hope, psychological adaptation and emotions in relation to a specified difficulty
- Increased resilience and decreased burn out in staff
- Enhanced interactions that are supportive and able to empower patients to be more autonomous
- Increased patient satisfaction
- Potential to decrease reliance on pharmacological approaches
- Reduced work absence and improved work productivity
- Identification of basic NHS-related cost savings

[figure not shown]

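### Objective 1 lists the pre-randomisation visit among the points at which the arms are compared. A difference there cannot reflect SIT, and counting that visit would shrink the estimated effect by a third if the decisive test is the group effect over all three visits.

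*Protocol*

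**What the plan says.** Under Aims and Objectives, Objective 1 treats depression and anxiety "as a primary outcome measure across three time points (pre-intervention, post intervention, at 12-weeks"). The instrument is the HADS: "A 14-Item questionnaire that assesses depression and anxiety". The objective's only between-arm sentence is "To compare the intervention and control at the pre-, post- and follow up time points". It gives the pre-intervention point the same standing as the other two, and nothing there limits it to a description of baseline.

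On timing, the Blinded assessor paragraph says "Before randomisation a blinded assessor (lecturer in physiotherapy or research student) will distribute questionnaires". Under Sequence generation, a person separate from the study "will allocate SHCP to an intervention control group using a random number generator". Data collection methods places the training after the baseline measurement.

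Statistical methods gives two quantitative analyses beyond descriptive statistics and confidence intervals. A factorial ANOVA "will be used to test group differences across outcome measures"; a parenthesis describes it as able to assess change in a single test. Separately, "An ANOVA will consider the change in scores across time for the intervention group". No baseline covariate, group-by-time term or decisive time point is named.

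**The concern.** Two things follow from listing the pre-intervention point as a between-arm comparison.

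First, the comparison is uninformative. With baseline taken before random allocation, the two arms are samples from the same population, and the null hypothesis at that visit is true by design. A difference there cannot bear on the stated aim, which is the impact of the training. An analysis plan that follows the objective literally would carry this comparison forward as part of the primary result.

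Second, the listing may affect the main test. If the group differences of the factorial ANOVA are read together with Objective 1 as the group main effect over the three listed visits, that effect averages in one visit where the true difference is zero. The estimate is pulled toward zero and power falls. Whether this happens depends on which term decides, and the protocol does not say.

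**Working it through.** **Inputs from the protocol (Sampling and sample size).** Alpha 0.01; d = 0.5, so SD = 1 on the standardised scale; 0.9 given as beta but evidently meant as power; 94 per group; 120, called a total; 140 per arm after adding 20; 280 in total.

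**Assumptions.** Two-sided testing; one intervention-versus-control comparison, as in the protocol's own calculation; equal SD at each visit; a common correlation rho between visits. The protocol gives no rho, so a range of 0.3 to 0.8 is shown.

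**Step 1: the protocol's own figure.** n per group = 2(z_0.995 + z_power)² / d².
- Power 0.9: 2 × (2.576 + 1.282)² / 0.25 = 119.04, so 120 per group.
- Power 0.8: 2 × (2.576 + 0.842)² / 0.25 = 93.4, so 94 per group.

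The stated 94 is therefore the 80% figure, and 120 is the 90% figure if read as per group. Since 120 + 20 = 140 per arm, the protocol itself uses 120 per arm although it calls it a total. The calculation below uses 120 per group; a single-visit t-test then has 89.8% power.

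**Step 2: size of the averaged effect.** With true effects 0, d1 and d2 at the three visits, the group main effect estimates (0 + d1 + d2)/3. That is two thirds of the post-baseline mean (d1 + d2)/2, whatever the split. With d1 = d2 = 0.5 it is 1.0/3 = 0.33 SD. This does not depend on rho.

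**Step 3: power at 120 per group, alpha 0.01 two-sided, noncentral t.**
- All three visits: difference 0.333, SD = sqrt((1 + 2rho)/3).
- Two later visits: difference 0.5, SD = sqrt((1 + rho)/2).
- Two later visits, baseline as covariate: difference 0.5, SD = sqrt((1 + rho)/2 − rho²).
- Mean of later visits minus baseline (the one-degree-of-freedom change contrast): difference 0.5, SD = sqrt((1 + rho)/2 + 1 − 2rho).

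| rho | Three visits | Two later visits | Later visits, baseline covariate | Change from baseline |
|---|---|---|---|---|
| 0.3 | 83% | 99% | 99% | 88% |
| 0.5 | 71% | 97% | >99% | 97% |
| 0.6 | 66% | 96% | >99% | 99% |
| 0.7 | 61% | 94% | >99% | >99% |
| 0.8 | 57% | 93% | >99% | >99% |

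Worked line at rho = 0.6: three-visit SD = sqrt(2.2/3) = 0.856 and standardised d = 0.333/0.856 = 0.39, giving 66%. For the two later visits, SD = sqrt(1.6/2) = 0.894 and d = 0.56, giving 96%.

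With all 140 per arm analysed, the three-visit figures are 89% (rho 0.3) to 66% (rho 0.8), still under 90%. With 94 per group they are 70% to 44%.

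**Step 4: simulation (4,000 runs, 120 per arm, rho 0.6).** The mean estimate of the three-visit group effect was 0.332 and its power 0.66. The group-by-time interaction had power 0.98. A test of the arms at the pre-intervention visit rejected in 0.85% of runs when SIT worked and 1.0% when it did not. It stays near the nominal 1% either way and carries no information about the effect.

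**The case against.** The strongest reply is that the protocol does not plan a test averaged over visits. Statistical methods says the ANOVA can assess change, and Objective 1 opens by exploring changes over the three points. A group-by-time comparison fits that wording, needs the baseline visit as its reference, and is not diluted. The choice of ANOVA term and the handling of baseline are also commonly settled in an analysis plan, which is not shown here. This stands, and it is why the power loss can only be stated conditionally. It does not rescue the objective, whose sentence compares the arms at each point, including one where no effect can exist.

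A reader might infer three stronger things that the documents do not support.
- That the trial is underpowered because of this wording. That requires the group main effect over three visits to be decisive, and no section says so.
- That baseline significance tests are planned. With four tests (two HADS subscales against two controls, taken as independent) the chance of at least one spurious result at 0.01 would be 1 − 0.99⁴ = 3.9%. But the protocol writes no such tests, a descriptive comparison also fits the objective, and tests sharing an intervention arm and related subscales are not independent.
- That baseline results will be used to select covariates or to discount a later effect. Nothing in the text says so.

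It is also fair to say that simply dropping the baseline visit is no clear improvement. At rho of 0.5 or more, the change contrast does as well as or better than comparing the later visits alone. The remedy should therefore keep baseline HADS in the model.

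**Conclusion.** The point holds in a limited form. Without any condition, Objective 1 includes a between-arm comparison on the primary outcome at a visit before randomisation, where a difference can only be chance, and this should be corrected. Conditionally, if the decisive test is the group main effect over all three visits, the estimate is two thirds of the post-baseline effect (0.33 rather than 0.50 SD). Power is then about 57% to 83% instead of the evidently intended 90%. Those power figures rest on 120 per group, two-sided alpha 0.01, equal effects at both later visits and an assumed rho of 0.8 to 0.3; the one-third shrinkage does not depend on rho. Under a group-by-time or baseline-adjusted analysis there is no dilution, although at rho 0.3 the change contrast itself has only about 88% power. Severity is minor to moderate.

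**What to change.** In Objective 1, remove the pre-intervention point from the between-arm comparison, so that intervention and control are compared on HADS at post-intervention and 12 weeks. Report baseline HADS by arm descriptively, with no significance test.

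In Statistical methods, state that the decisive between-arm comparison is HADS at those two visits with baseline HADS as a covariate. Under the assumptions above, the average over both visits then has about 99% power or more. If the investigators prefer a group-by-time analysis, that is also valid, but the protocol should name it as the deciding term.

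Cost: two sentences. The baseline questionnaire is still needed, as the covariate and for describing change, and no new data are required.

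While editing, reconcile 94, 120 and 140 in the sample-size paragraph, since any power statement depends on which is meant.

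### The sample-size figures do not follow from one another: 94 per group gives about 80% power, not 90%; 120 is a per-group number called a total; and 280 covers two arms where the design describes three

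*Protocol*

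**What the plan says.** The calculation is in the protocol under Main Study, Sampling and sample size. It cites Cohen's tables "with an alpha of 0.01" and a standardised difference of 0.5, and goes on: "beta of 0.9 we will recruit 94 SHCP per group to take part in this research. This will give a total of 120 SHCP". Next comes the allowance for loss: "we will add in a 10% margin ($n=20$) for dropout or incomplete data". The paragraph closes: "This gives a total of 140 SHCP to be randomised per arm or 280 in total".

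The number of arms has to be read from elsewhere. The Design paragraph names both an inactive waiting-list control and an active control. The Intervention section describes them separately as control groups 1 and 2, alongside the SIT intervention. The primary outcome is the Hospital Anxiety and Depression Scale (HADS).

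**The concern.** A sample-size paragraph should run in one line from error rates and effect size to evaluable number, dropout allowance, number randomised per arm and total. Here four numbers (94, 120, 140, 280) are offered as successive steps, and the early steps do not lead to the later ones. The first is tied to a power that it does not deliver, the second carries the wrong unit, and the dropout percentage does not match its own count. The final total fits two arms, although the design has three groups.

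What is at stake is the power of the primary comparison. A team that works to 94 per group, or spreads 280 over three arms, would be following the text and yet run at roughly 80% power or less while reporting 90%.

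**Working it through.** **Inputs.** From Sampling and sample size: alpha 0.01, d = 0.5 (so SD = 1), beta written as 0.9, 94 per group, 120 in total, a margin of 20 labelled 10%, 140 per arm, 280 in total. From Design and Intervention: one intervention group and two control groups.

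**Assumptions.** Sidedness is not stated; two-sided is taken as the default and one-sided is shown as well. The beta is read as power 0.90, because a literal beta of 0.9 means 10% power and would need only 14 per group.

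**Step 1: reproduce 94.** n per group = 2(z₁₋α/₂ + z_power)² / d².
- Power 0.80: 2(2.576 + 0.842)² / 0.25 = 93.4, so 94 (t-based 95.1).
- Power 0.90: 2(2.576 + 1.282)² / 0.25 = 119.0, so 120 (t-based 120.7, so 121).
- Power 0.90, one-sided: 2(2.326 + 1.282)² / 0.25 = 104.1, so 105.

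The stated 94 is therefore the two-sided answer for 80% power. The stated 120 is the two-sided per-group answer for 90% power.

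**Step 2: power at the candidate numbers.** Two-sided, alpha 0.01, d = 0.5; power ≈ Φ(d√(n/2) − 2.576), with the noncentral-t value beside it.

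| n per group | Normal | t |
|---|---|---|
| 84 | 74.7% | 73.6% |
| 93 | 79.8% | 78.9% |
| 94 | 80.3% | 79.4% |
| 120 | 90.3% | 89.8% |
| 140 | 94.6% | 94.3% |

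One-sided power at 94 per group is 86.5% (normal) or 85.9% (t), still short of 90%.

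**Step 3: totals.** 2 × 94 = 188 and 3 × 94 = 282. Neither is 120.

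**Step 4: dropout.** 20/120 = 16.7%, and 20/140 = 14.3%. A 10% loss calls for 120/0.9 = 133.3, so 134 per arm.

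**Step 5: arms.** 2 × 140 = 280, but 3 × 140 = 420. Spread over three arms, 280/3 = 93.3 each, and 93.3 × 0.9 = 84 evaluable after a 10% loss. From the table, t-based power per pairwise comparison is then about 79% before dropout and about 74% after it.

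**The case against.** The strongest reply is that the paragraph ends with an explicit target of 140 per arm and 280 in total. If 120 is read as per group, then 120 + 20 = 140 and 2 × 140 = 280, so three of the four numbers form a chain. For two arms that target gives about 94% power, or 90% after losing 20 per arm. This stands. A reader might infer that the recruitment target is undefined or that the trial is underpowered outright; the documents do not support that for two arms. Nor should weight be put on a stop at 120 in total (55% power over two groups, 35% over three), because the next two sentences go beyond it.

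A second reply is that 94 may come from another calculation. A three-group one-way ANOVA with f = 0.25 at alpha 0.01 has 89.8% power at 94 per group, and 3 × 94 = 282 is close to 280. But the protocol states d, not f. With d = 0.5 between the intervention and two equal controls, f is 0.236 and that ANOVA has 85% power. It then goes on to 140 per arm, which this route does not explain. It is a reason to ask which number is the target, not a reconciliation.

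Third, the control side might be one arm of 140 divided between the two controls; Appendix A speaks of a control group that either views a lecture or has no treatment. Pooled, that keeps 94% power. Against each control separately, 140 versus 70 gives about 79% (t-based, before dropout). The protocol does not say that this is the plan.

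Finally, 20 is close to 10% of 188 (10.6%), but the text adds it to 120.

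**Conclusion.** The paragraph is wrong as written in three places: 94 per group does not go with power 0.90, 120 is not a total, and 20 is not a 10% margin. The shortfall at 94 per group is about 10 percentage points two-sided, or about 4 one-sided.

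Whether the trial itself falls short depends on the number of arms. With two arms of 140 it meets its stated power. With three arms sharing 280, each pairwise comparison has about 79% power before dropout and about 74% at 84 evaluable per arm. The paragraph does not say which applies, and the design sections point to three groups.

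These figures rest on a two-sided test, equal allocation, pairwise comparison at alpha 0.01 without further adjustment, and d = 0.5 holding for HADS. The last is an assumption: the pilot result cited in the paragraph concerns communication, and no pilot effect on HADS is given.

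**What to change.** Rewrite the paragraph as one chain:
- Alpha 0.01 with its sidedness stated; power 0.90 (beta 0.10); d = 0.5 labelled as an assumption for HADS.
- If two-sided, 120 evaluable per arm (121 on the t-test).
- The actual dropout allowance: 134 randomised per arm at 10% loss, or 140 per arm at 14%.
- The number of arms, which comparison the calculation is for, and the matching total.

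Remove the 94 and the words that make 120 a total. If 94 per group is the real target, keep it and state about 80% power.

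**Cost.** For two arms this is wording only: 280 at 140 per arm, or 268 at 134. For three arms at 90% power the total rises to 402 (122 more than stated) or 420 (140 more). If 280 must cover three arms, no one is added, but the power should be restated as about 79% before dropout and about 74% after 10% loss, per pairwise comparison.

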The planned study requires SHCP to be allocated to either a control group or the intervention group (with MEAH training). SHCP assessment will take place before and after the intervention and again at 12-weeks. The waiting list control group will receive the MEAH training at 12-weeks. Follow up assessment for both groups will be at 3 months. The main purpose of this study is to investigate the content of the SIT e-learning training on SHCP and gain an insight into the effect of this inexpensive and accessible, evidence-based training on patient outcomes. The most direct benefits include; (a) improved mental health for SHCP and patients. (b) empowerment of patients to seek positive coping behaviours, reducing the need for additional costly healthcare services for SHCPs and potentially patients. (c) increase resilience of SHCP and reduced burn out (d) improve patient satisfaction and (e) reduced need for pharmacological approaches to treat mental illness SHCP (f) reduced work absence and improved productivity of SHCP .

Introduction

Understanding and supporting the mental health of frontline workers during the COVID-19 is fundamental to the health of staff and patients. Within the hospital setting SHCP face

environments of extreme stress caused by COVID-19, this includes access to appropriate personal protective equipment, being deployed to new and unknown practice environments, a lack of updated information, being exposed to the virus and then concerns about perhaps unknowingly transmitting to a family member, peers or others (Shanafelt et al., 2020). Outside the work setting opportunities to support others within their family circle are impacted by government legislation of lockdown and social distancing. As a result, SHCP are experiencing profound psychological problems, including anxiety, depression and distress; a direct result of caring for patients who have COVID-19 (Pfefferbaum and North, 2020; Lui et al., 2020).

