 4. To identify any differences between SHCP cohorts (e.g. doctors, speech and language therapist, nurses, occupational therapists and physiotherapists)
- To illuminate the benefits of our e-learning approach on the SHCP mental health.

Main Study

We report this according to the SPIRIT guidelines (Chan et al., 2013).

Design: A multi methods study involving a randomised trial with a waiting list inactive and active control group. Following the CONSORT recommendations and flow diagram (Schulz et al., 2010). See Figure 1 for trial design and Table 1 for Gantt Chart. Qualitative data will be generated through the training which will further help understanding experiences of COVID-19 and a qualitative study involving semi-structured interviews to consider the benefit of the study will be undertaken from week 12. PPI involvement has contributed to this across different stages see below.

Study setting: The trial will be run from the following Universities: University of Birmingham, Birmingham City University, Coventry University, Brighton University, Southampton University and Oxford Brookes University.

Contacts at the following Universities have been made to agree access:

University of Birmingham

Existing contacts: [name], [name], [name] – Physiotherapy here at Birmingham

New requests: Nursing – [name], Medicine – [name].

Brighton University – [name] Physiotherapy Program

Southampton University - [name] lecturer in health sciences here and PT, and [name]

Birmingham City University - [name] Speech and Language therapy course lecturer.

Oxford Brookes University. - [name] (programme Lead) and [name] (Subject coordinator) for the physio programmes at Brookes.

Coventry University for Occupational Therapy Program – [name] [name]

Nottingham University – Occupational Therapy [name].

Eligibility; Any SHCP currently **studying at on a course from the above Universities.**

Approach and Recruitment; An initial email contact (Appendix A) will be sent to all SHCP with an information sheet via email (See Appendix B). After 48 hours individuals will be recruited.

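### The protocol describes three groups but sizes two, and 280 participants cannot give 90% power for SIT against each control separately

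*Protocol*

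**What the plan says.** **Three groups.** Main Study, Design, describes "a randomised trial with a waiting list inactive and active control group". The text after Intervention then defines the two controls under separate numbered labels: group 1 is an inactive waiting list, and for the second it says "Active control group 2: an alternative e-intervention will be used which includes a 45 minutes pre recorded lecture". Appendix A tells prospective participants that those in the control group will either watch a lecture or have no treatment.

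**Two groups.** The opening summary says "The planned study requires SHCP to be allocated to either a control group or the intervention group". Objective 1 compares the intervention with one unspecified control, and the second Sequence generation paragraph is also worded for intervention and control only. Sampling and sample size uses "tables with an alpha of 0.01", d = 0.5, "and beta of 0.9 we will recruit 94 SHCP per group to take part in this research", then moves to 120, adds 20 for dropout and ends with "This gives a total of 140 SHCP to be randomised per arm or 280 in total".

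**Analysis.** Statistical methods plans a factorial ANOVA of group differences. It does not say which control the primary comparison uses.

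**The concern.** The number of arms, the total randomised and the sample size basis are fixed in the protocol, and they do not fit together. With three arms, 140 per arm and 280 in total cannot both be true.

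Two things are at stake. First, if recruitment stops at 280 and each control is compared with SIT, a null result would come from a comparison with materially less than the stated power. Second, SIT could be set against the waiting list, against the lecture, or against both combined. While none of these is named as primary, a favourable result on any of the three could be presented as the main finding.

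**Working it through.** **Inputs.** From Sampling and sample size: alpha 0.01, d = 0.5, a stated 0.9 read as power, a 10% dropout margin given as n = 20, 140 per arm, 280 in total. Assumed: a two-sided test, because it reproduces the protocol's 120 (one-sided gives 105). The allocation ratio is not stated, so 1:1:1 and 2:1:1 are both shown.

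**Reproducing the plan's figure.** For two equal groups, n per group = 2(z₀.₉₉₅ + z_power)² / d².

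- 90% power: 2(2.576 + 1.282)² / 0.25 = 119.0, so 120 per group. Adding 20 gives 140, and 2 × 140 = 280. The total reproduces, but only for two groups.
- 80% power: 2(2.576 + 0.842)² / 0.25 = 93.4, so 94. The stated 94 per group is therefore the 80% figure and conflicts with the 120 that follows it.
- Dropout: 20/120 = 16.7% and 20/140 = 14.3%; neither is 10%. A 10% loss needs 120/0.9 = 133.3, so 134 per arm.

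**Power at 280.** Power ≈ Φ(d√[n₁n₂/(n₁+n₂)] − 2.576). For 84 v 84 this is Φ(0.5√42 − 2.576) = Φ(0.665) = 0.747. The t-based value is slightly lower.

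| Reading of 280 | Compared | Normal | t-based |
|---|---|---|---|
| Controls pooled as one arm of 140, 20 lost per arm | 120 v 120 | 90.3% | 89.8% |
| Controls pooled after 1:1:1, 10% loss | 84 v 168 | 87.8% | 87.3% |
| 1:1:1, no loss | 93 v 93 | 79.8% | 78.9% |
| 1:1:1, 10% loss | 84 v 84 | 74.7% | 73.6% |
| 1:1:1, 14.3% loss | 80 v 80 | 72.1% | 71.0% |
| 2:1:1, no loss | 140 v 70 | 80.0% | 79.2% |
| 2:1:1, 10% loss | 126 v 63 | 74.7% | 73.8% |
| 2:1:1, 14.3% loss | 120 v 60 | 72.1% | 71.1% |

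**Could another split serve both comparisons?** For any SIT group size, the weaker comparison is strongest when the two controls are equal. Searching over SIT sizes on that basis, the best is about 117 in SIT: 81.3% with no loss and 76.2% after 10% loss (normal approximation). So no split of 280 gives 90% for both. One comparison alone can be served: 120/120/40 with no loss gives about 90% for 120 v 120, but for 120 v 40 it gives Φ(0.5√30 − 2.576) = Φ(0.163), about 56%.

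**Detectable effect at 90% power, 84 v 84.** (2.576 + 1.282)√(2/84) = 0.595; t-based 0.601. Call it 0.60, against the planned 0.50.

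**Total needed for 90% on each comparison.** At 1:1:1: 3 × 120 = 360 evaluable; 3 × 134 = 402 randomised at 10% dropout; 3 × 140 = 420 at the protocol's own 140 per arm. At 2:1:1: 4 × 90 = 360 evaluable, 360/0.9 = 400 randomised.

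**The case against.** The best defence is that 280 is correct because the two controls form one arm. The summary, Objective 1 and the randomisation text all speak of intervention and control, and Appendix A first offers those two outcomes and only then divides the control group. On that reading, with SIT taking half of the participants, the stated power is met. Alternatively, 140 per arm may be meant literally, in which case each comparison is adequately sized and only the total is wrong. The missing Figure 1 may show which was intended.

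This stands as far as it goes. A reader might infer that the trial is underpowered against both controls whatever was meant; the documents do not support that. What they show is an unresolved contradiction, with a shortfall under some readings and not others. Pooling would also leave neither control separately tested at 90%, and the text nowhere says that pooling is planned.

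It can also be said that the primary contrast belongs in a statistical analysis plan. It may be named there, but the number to recruit depends on it and is fixed here.

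Two further inferences should be resisted. "Only blinded assessment will take place" might be read as a claim that the self-completed primary outcome is blinded. It stands under the Blinded assessor heading and concerns the staff who distribute and collect questionnaires, so it is no contradiction. Nor does the protocol propose dividing alpha between the two controls, so lower power figures based on such a split do not describe this plan.

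**Conclusion.** The concern holds as an inconsistency in the number of arms, the total and the control structure. The sample size calculation is a two-group one applied to a three-group description. If 280 stands and each control is compared with SIT at 1:1:1 or 2:1:1, power per comparison is about 79% with no loss and about 74% after 10% loss, against about 90% for the two-arm reading.

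These figures rest on three assumptions: 0.9 means power, the test is two-sided, and the ratio is one of the two shown. They also carry over d = 0.5 for both contrasts. The protocol's "a medium effect size is expected" follows a remark on pilot results for student communication, not for the HADS against an active lecture.

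**What to change.** 1. State the number of arms and the allocation ratio consistently in the summary, objectives, design, randomisation text and Appendix A.
2. Reconcile 140 per arm with 280 in total, by one of these routes:
   - Keep 280 with separate comparisons and restate the size and power. At 1:1:1 that is about 93 randomised and 84 evaluable per arm, about 74% power and a detectable d of about 0.60.
   - Keep 280 and state that the controls are pooled, with the share allocated to SIT, and that neither control is then tested separately at 90% power.
   - Keep 90% per comparison and raise the total to about 402 randomised at the stated 10% dropout, or 420 at the protocol's own 140 per arm.
3. If the controls are kept separate, name one control contrast as primary before randomisation and test the other second in fixed order at the same alpha. SIT versus the active control is one reasonable choice, not the only one.
4. In the same paragraph, reconcile 94 with 120 per group, present 120 as a per-group number, describe 0.9 as power, and bring the 20 extra participants into line with the 10% margin.

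The first two routes cost only wording, plus either a less favourable stated power or the loss of separately powered control comparisons. The third costs about 122 more participants (402 − 280), or 140 more at 420.
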